5.3.5 Handling of Missing Data, Dropouts, and Outliers

No imputation will be performed for missing data.

Data exceptions will be identified before data base lock based on discussion with medical experts if necessary.

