5.4.2 Secondary Efficacy Analyses

• Analysis of PFS

PFS will be summarized by Kaplan-Meier method using median with 95% CI. Kaplan-Meier curve will be provided. The number of event/censor (percentage) will be also summarized.

• Analysis of DOR

DOR will be summarized by Kaplan-Meier method using median with 95% CI in responders. The number of event/censor (percentage) will be also summarized.

• Analysis of TTR

TTR will be summarized using descriptive statistics in responders.

• Analysis of CR rate

Best overall response will be summarized. For CR rate (the rate of subjects whose best overall response is CR) Exact 95% CI will also be provided.

• Analysis of OS

OS will be summarized by Kaplan-Meier method using median with 95% CI. Kaplan-Meier curve will be provided. The number of event/censor (percentage) will be also summarized. In addition, summarization for follow-up time will be provided using Kaplan-Meier method.

PFS will be calculated as: End date for PFS – Date of administration of the first dose of study drug + 1 (day) DOR will be calculated as: End date for DOR – Date of the first response + 1 (day)

End date of PFS and DOR is defined as the table below:

Situation	End Date for PFS and DOR	Censored
Documented progression disease (PD) during the study	Date of the first assessment of the series of the tests that determined PD	No
Death during the study before PD	Date of death	No
No baseline assessments	Date of administration of the first dose of study drug	Yes
Treatment discontinuation without post- baseline tumor assessments	Date of administration of the first dose of study drug	Yes
New anticancer treatment started prior to disease progression	Date of last tumor assessment before start of new treatment	Yes
Death or PD after more than one missed tumor assessments	Date of the last tumor assessment before missed assessments	Yes
Subjects still on treatment without PD as of data cut-off	Date of last tumor assessment	Yes

TTR will be calculated as: Date of first response – Date of administration of the first dose of study drug + 1 (day)

OS will be calculated as: End date for OS – Date of administration of the first dose of study drug + 1 (day)

End date for OS is defined as the table below:

Situation	End Date for OS	Censored
Death during the study	Date of death	No
Alive at cut-off	Date of cut-off	Yes
Other than the above	Last known alive date	Yes

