5.6.2 Adverse Events

The AE verbatim descriptions (investigator terms from the CRF) will be classified into standardized medical terminology using the Medical Dictionary for Regulatory Activities (MedDRA). AEs will be coded to the MedDRA (Version 19.1 or higher) lower level term (LLT) closest to the verbatim term. The linked MedDRA preferred term (PT) and primary system organ class (SOC) will also be captured in the database.

A treatment-emergent adverse event (TEAE) is defined as an AE that emerged on or after the date of first dose of study drug, having been absent at pretreatment (Baseline) or

• Reemerged during treatment, having been present at pretreatment (Baseline) but stopped before treatment, or

• Worsened in severity during treatment relative to the pretreatment state, when the AE was continuous.

Only those AEs that are treatment emergent will be included in summary tables. All AEs, treatment emergent or otherwise, will be presented in subject data listings.

Over view of TEAEs and treatment-related TEAEs include the number and percentage of subjects with any TEAEs, treatment-related TEAE, TEAEs with grade 3 or higher, serious TEAEs (death, other SAEs) and TEAEs leading to study drug dose adjusment (study drug withdrawal, dose reduction, interruption).

The number and percentage of subjects with TEAEs will be calculated from the following viewpoints.

- All/Treatment-related TEAEs by PT
- All/Treatment-related TEAEs by SOC/PT
- All/Treatment-related TEAEs with Grade 3 or Higher by PT
- All/Treatment-related TEAEs with Grade 3 or Higher by SOC/PT
- All/Treatment-related TEAEs by SOC/PT and Grade
- All/Treatment-related TEAEs with Grade 3 or Higher by SOC/PT and Grade
- All/Treatment-related Serious TEAEs by PT
- All/Treatment-related Serious TEAEs by SOC/PT
- All/Treatment-related Serious TEAEs by SOC/PT and Grade

- All/Treatment-related TEAEs leading to withdrawal by SOC/PT
- All/Treatment-related TEAEs leading to dose reduction by SOC/PT
- All/Treatment-related TEAEs leading to dose interruption by SOC/PT
- All/Treatment-related TEAEs leading to delay by SOC/PT
- Specially grouped TEAE by SOC and PT
- Specially grouped TEAE by SOC and PT and Cycle
- Specially grouped TEAE with Grade 3 or Higher by SOC and PT
- Specially grouped TEAE with Grade 3 or Higher by SOC and PT and Cycle

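### Does the no-imputation rule drop adverse events and deaths with incomplete dates from the analysis?

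*SAP*

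**What the plan says.** Section 5.3.5 states "No imputation will be performed for missing data", and section 8.2 repeats the sentence. Neither section mentions dates.

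Three definitions use dates:

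- **Adverse events (5.6.2).** A treatment-emergent event "is defined as an AE that emerged on or after the date of first dose of study drug" and was absent at baseline; re-emergence or worsening during treatment also qualifies. Then: "Only those AEs that are treatment emergent will be included in summary tables". And: "All AEs, treatment emergent or otherwise, will be presented in subject data listings".
- **OS (5.4.2).** "OS will be calculated as: End date for OS" minus the first-dose date plus one day. The end-date table has an event row, "Death during the study Date of death No", a row for subjects alive at cut-off, and a residual row, "Other than the above Last known alive date Yes".
- **Progression-free survival (PFS) and duration of response (DOR) (5.4.2).** Death before progression ends on the date of death. New anticancer treatment censors at the last tumour assessment before it began.

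The opening of section 8 leaves data handling to a sponsor decision before database lock. Section 9 places derivation rules in separate documents, which are not shown.

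**The concern.** An unknown day of onset or death is missing data in the ordinary sense, and completing it is a form of imputation. Read literally, a rule stated twice without exception would forbid completing it.

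Two consequences would matter. An adverse event whose onset cannot be placed on or after first dose might never reach a summary table, so incidence would be understated. A death without a full date cannot be entered in a day-level subtraction. If that subject were moved to the row headed "Other than the above", a known death would become a censored time. Both would flatter the drug. The first would also sit oddly with section 7, which says that the treatment-emergent definition was changed to be conservative. A partial start date for new anticancer treatment could leave a PFS censoring date open in the same way.

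**Working it through.** No figure in the SAP bears directly on this point, so the main check is textual, with a small illustration for adverse events.

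**1. Deaths in OS.** The first column of the end-date table is the subject's situation, not whether a date can be computed.

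| Situation | Does a known on-study death with an incomplete date fit? |
|---|---|
| Death during the study (event) | Yes |
| Alive at cut-off (censored) | No |
| Residual row (censored at last known alive date) | No, because an earlier row already applies |

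The event status is therefore fixed. What is open is the day, and for a death known to the month that is at most about 30 days of one subject's time. The same holds for the death row of PFS and DOR.

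**2. New anticancer treatment.** The censoring date is the last tumour assessment before the new treatment. A partial start date leaves it open only if an assessment falls inside the span that the known part of the date allows. Otherwise the last prior assessment is the same whichever day is assumed.

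**3. Adverse events.** Suppose the onset month is known and the day is not.

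- Month after the first-dose month: onset is after first dose, with no imputation.
- Month before it: onset is before first dose, with no imputation.
- Same month: the date alone does not decide.

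A wholly missing date, or a year-only date in the year of first dose, is also undecided.

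How often does the same-month case arise among events that truly began on treatment? Assume first dose on day *d*, uniform on 1 to 30 of a 30-day month, and onset *k* days later, uniform on 0 to *T* − 1, where *T* is days of treatment. The case is ambiguous when *d* + *k* ≤ 30. For each *k* from 0 to 29 there are 30 − *k* such values of *d*, so

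share = Σ(30 − *k*) / (30 × *T*), summed over *k* from 0 to min(*T* − 1, 29).

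| Days of treatment *T* | Calculation | Share ambiguous |
|---|---|---|
| 21 (1 cycle) | 420 / 630 | 67% |
| 42 (2 cycles) | 465 / 1260 | 37% |
| 84 (4 cycles) | 465 / 2520 | 18% |
| 168 (8 cycles) | 465 / 5040 | 9% |

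The 21-day cycle and the maximum of 8 cycles come from section 3.2 (8 × 21 = 168). These are shares of month-only onsets, not of all adverse events; the SAP does not say how many onsets are month-only.

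**4. The ambiguous events.** Section 5.6.2 says nothing about excluding them. Its definition also uses absence at baseline, and section 3.2 puts the baseline assessment within 7 days before treatment. If an event was absent at that assessment, the only pre-dose days on which it could have begun are those few. Classing it as treatment-emergent is the natural reading, and the event is listed either way.

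**5. Size per subject.** With the 35 subjects of section 4, one subject is 1/35 = 2.9 percentage points. In the CTCL group, with its target of 6, it is 1/6 = 16.7 points. To produce such a shift, a subject's only event of that type must have an ambiguous onset and must then be left out, a step the SAP does not prescribe.

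**The case for a change.** The strongest case for a change is that the SAP is not merely silent. It gives a blanket rule and repeats it in section 8.2, where a date convention would normally sit. A rule in the separate derivation documents that completes partial dates would then conflict with that sentence. The trial is open-label with a single arm, so a decision taken just before lock is taken with outcomes visible. Ambiguous onsets also cluster in early treatment, and results are reported by disease in small groups.

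Some of this stands. The SAP shown has no partial-date convention, and taken literally the sentence leaves the exact day of an incompletely dated death undefined. But the sentence speaks of missing data, and extending it to partly known dates is an inference. Classifying an event from the known part of its date is not imputation. The scope for a choice that favours the drug is also narrow: a known death remains an event under the table, so only its day within a known span can move. For adverse events, exclusion would need a rule that the SAP does not contain. The remark in section 7 concerns the definition of a treatment-emergent event, not date handling; if anything, it points analysts towards inclusion.

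**Conclusion.** The concern does not call for a change. The SAP leaves a routine convention unwritten, but its text does not censor deaths with incomplete dates and does not remove adverse events from the tables. What stays open is the exact day of an incompletely dated death, the status of adverse events whose onset is wholly missing or known only to the month or year of first dose, and an occasional PFS or DOR censoring date. Analysts settle such cases before lock under the arrangements in sections 8 and 9.

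No direction of bias is shown. The size cannot be stated beyond 2.9 points per affected subject in 35, because the frequency of partial dates is not given. The 67% to 9% range rests on uniform onset over treatment and a uniform first-dose day in a 30-day month. The objective response rate in section 5.4.1 and the sample size in section 4 do not depend on any of this.

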5.4 Efficacy Analyses

FAS will be the primary analysis population. All efficacy result will be summarized for each disease and overall. Results from central assessment by efficacy and safety evaluation committee and investigator assessment will be used, as applicable. If needed, efficacy analysis results per investigator assessment will also be summarized. Unless otherwise noted, overall response considering both "Revised Response Criteria for Malignant Lymphoma (Cheson, J Clin Oncol; 2007)" and "Clinical Endpoints and Response Criteria in Mycosis Fungoides and Sézary Syndrome (Olsen, J Clin Oncol; 2011)" will be used.

For summarization of tumor assessment relevant analysis except PFS and DOR, assessment results until discontinuation from study treatment will be used.

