3.2 Overall Study Design and Plan

This is a multicenter, single-arm, open label, Phase 2 to evaluate efficacy, safety, PK and immunogenicity of E7777 in patients with relapsed or refractory PTCL and CTCL. This study composed of the following 3 periods: preparation, treatment and follow-up periods. The preparation period consists of the following four procedures: informed consent (IC), screening, enrollment, and baseline assessment. Informed consent (IC) is able to obtain 28 days before the treatment. Enroll the patient who meet the inclusion criteria and does not meet the exclusion criteria. Conduct the baseline assessment within 7 days before the treatment. Confirm that the patient continue to meet the inclusion criteria and does not meet the exclusion criteria before moving to the treatment period. The

treatment period consists of 1 cycle of 3 weeks and lasts until meet the "discontinuation criteria" or Day 21 of Cycle 8. The evaluation at discontinuation will be performed within 7 days after termination of study treatment.

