4 DETERMINATION OF SAMPLE SIZE

Thirty-five patients were required to detect lower limit of the 95% confidence interval (CI) that exceed the 5% threshold in ORR, which is the primary endpoint of the study, with the expected ORR is 25% with a statistical power of 90%. In CTCL, 6 or more patient is targeted to evaluate the safety as specific disease.

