5.2 Study Subjects

5.2.1 Definitions of Analysis Sets

Full Analysis Set (FAS):

Defined as a group of subjects who have received at least one dose of the study drug. This group will be the population for the evaluation of efficacy.

Safety Analysis Set:

Defined as a group of subjects who have received at least one dose of the study drug with at least one evaluable post-baseline safety data. This group will be the population for the evaluation of safety.

Pharmacokinetics Analysis Set:

Defined as a group of subjects in who have received at least one dose of the study drug with at least one serum concentration data.

Pharmacodynamics Analysis Set:

Defined as a group of subjects in who have received at least one dose of the study drug with at least one evaluable pre and post-baseline PD data.

On eligibility-confirmed subjects, the number (percentage) of subjects included in each analysis set will be summarized.

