5.4.1 Primary Efficacy Analyses

The rate of subjects whose best overall response is CR or PR is calculated as ORR, and the Exact 95% CI is also calculated. Analysis based on central assessment by Efficacy and safety evaluation committee will be regarded as primary result.

Additionally, For PTCL, best overall response and ORR using overall response evaluated according to "Revised response criteria for malignant lymphoma" will be summarized. And for CTCL, best overall response and ORR based on global response score of "Clinical end points and response criteria in mycosis fungoides and Sézary syndrome" will be summarized.

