7 CHANGES IN THE PLANNED ANALYSES

The list below includes both change from protocol and SAP version 1.0.

- Summarization of "Analysis Sets" has been added (section 5.2.1).
- Summarization of "Completion and discontinuation for treatment" has been deleted because the data is not collected (section 5.2.2).
- Summarization of "CCR4 category", "each disease histology and each stage" and "Relapsed/Refractory status" has been added (section 5.2.3).
- Summarization of "Number of previous systemic chemotherapy regimen" and "each previous systemic chemotherapy" has been added (section 5.2.4).
- Summarization of "prior medication" and "concomitant medication" has been deleted (section 5.2.4).
- Definition of concomitant medication has been changed (section 5.2.4).
- Summarization of "Treatment Compliance" has been added (section 5.2.5).
- Subgroup analyses for efficacy and safety have been added (section 5.3.4).
- Summarization of efficacy endpoints by investigator has been added (section 5.4).
- Handling rule of tumor assessment data has been clarified (section 5.4).
- Summarization of "BOR and ORR focused on PTCL/CTCL evaluation criteris" has been added (section 5.4.1).
- Summarization of "Event/censor" for PFS, DOR and OS has been added (section 5.4.2).
- Kaplan-Meier curve for PFS, OS and OS has been added (section 5.4.2).
- Censoring rule for PFS and DOR has been changed (section 5.4.2).
- Summarization of TTR has been changed to not use Kaplan-Meier method because there is no need to use Kaplan-Meier method if the target is responder. (section 5.4.2).
- Summarization of "Best overall response" has been added (section 5.4.2).

- Summarization of "Best overall response and ORR for each disease histology" has been added (section 5.4.3).
- Summarization of "Best response for each lesion" has been added (section 5.4.3).
- Waterfall plot of "target lesions and mSWAT score" has been added (section 5.4.3).
- Spider plot of "target lesions and mSWAT score" has been added (section 5.4.3).
- Plotting individual values of immunogenity titer and PD markers on mean plot has been deleted (section 5.5.2).
- Summarization of "dose ratio" has been changed to "relative dose intensity" (section 5.6.1).
- Definition of TEAEs has been changed to be conservative (section 5.6.1).
- Detailed listing of AE tables has been added (section 5.6.2).
- Some patterns of summazation on TEAEs has been added (section 5.6.2).

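### Does ending the ORR window at treatment discontinuation drop responses first seen at the discontinuation evaluation?

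*SAP*

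**What the plan says.** Section 5.4 (Efficacy Analyses) states: "For summarization of tumor assessment relevant analysis except PFS and DOR, assessment results until discontinuation from study treatment will be used". Section 5.4.1 gives the primary endpoint no window of its own: "The rate of subjects whose best overall response is CR or PR is calculated as ORR, and the Exact 95% CI is also calculated". The Section 5.4 sentence therefore governs best overall response and ORR, and also CR rate and TTR in Section 5.4.2.

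Section 3.2 ends the treatment period when discontinuation criteria are met "or Day 21 of Cycle 8", and adds: "The evaluation at discontinuation will be performed within 7 days after termination of study treatment".

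Section 7 reports that a summary of treatment completion and discontinuation "has been deleted because the data is not collected (section 5.2.2"). It also lists the tumor-assessment handling rule in Section 5.4 as a clarification.

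Section 4 gives the design: "Thirty-five patients were required to detect lower limit of the 95% confidence interval (CI) that exceed the 5% threshold in ORR", "with the expected ORR is 25% with a statistical power of 90"%. The denominator is the FAS (Section 5.2.1): "Defined as a group of subjects who have received at least one dose of the study drug".

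**The concern.** The sentence in Section 5.4 decides who counts as a responder, yet it ties discontinuation to no date or visit. If a programmer took the termination date, or the last-dose date, as a hard cut-off, an assessment made a few days later at the discontinuation evaluation would fall outside. A first response seen there, or an upgrade from PR to CR, would not count towards ORR or CR rate.

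Three features add to the unease.

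- Section 7 can be read as saying that the anchor for the window is not collected.
- Subjects who reach Day 21 of Cycle 8 complete treatment rather than discontinue it. Read literally, their window has no stated end, and the sentence does not exclude assessments after new anticancer treatment.
- PFS and DOR are exempt from the window, so they draw on assessments that ORR does not use.

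Each response is worth 1/35 = 2.9 percentage points of ORR, and a single response can decide whether the lower confidence limit clears 5%.

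**Working it through.** **The plan's own figure.** Inputs from Section 4 are N = 35, threshold 5%, expected ORR 25% and power 90%. Section 5.4.1 specifies an exact 95% CI. The Clopper-Pearson lower limit for x responders of n is the 2.5% quantile of Beta(x, n − x + 1).

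- x = 5: 5/35 = 14.3%, CI 4.8% to 30.3%; does not exceed 5%.
- x = 6: 6/35 = 17.1%, CI 6.6% to 33.6%; exceeds 5%.

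Success therefore needs at least 6 responders. P(X ≥ 6 | n = 35, p = 0.25) = 0.9024, and P(X ≥ 6 | n = 35, p = 0.05) = 0.0073. The stated 90% power reproduces, and it does not depend on how the window is worded.

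**What a loss would cost, if there were one.** Suppose a share f of responses is first documented at the discontinuation evaluation and then excluded. The counted response rate becomes 0.25 × (1 − f). The SAP gives no value for f, so this is an assumed range. The expected number of responders without loss is 35 × 0.25 = 8.75.

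| Assumed f | Counted rate | Expected responders lost (8.75 × f) | P(X ≥ 6) |
|---|---|---|---|
| 0 | 25.00% | 0 | 90.2% |
| 2% | 24.50% | 0.18 | 89.1% |
| 5% | 23.75% | 0.44 | 87.1% |
| 10% | 22.50% | 0.88 | 83.1% |
| 15% | 21.25% | 1.31 | 78.4% |
| 20% | 20.00% | 1.75 | 72.8% |

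Requiring 7 true responders instead of 6 gives 80.8%. That assumes one responder is lost in every realization of the trial, so it is not an estimate of the plan's power.

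**Whether the SAP creates the loss.** Two conditions must both hold.

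1. *The window closes before the evaluation.* Section 5.4 runs the window until discontinuation. Section 3.2 calls the visit the evaluation at discontinuation and allows 7 days to perform it. Nothing in the SAP excludes that visit or defines a date filter, and including it is at least as natural a reading.
2. *A tumor assessment is made there.* The SAP does not say so. Assessment schedules commonly sit in the protocol, which is not shown.

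**The anchor.** The Section 7 item explains why one disposition table was removed from Section 5.2.2. It does not say that treatment dates are unavailable. Section 5.6.1 summarizes duration of treatment and cycles received, and the PFS/DOR table in Section 5.4.2 uses treatment discontinuation as a censoring situation.

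**Completers.** Section 3.2 ends the treatment period at Day 21 of Cycle 8 and times the evaluation from termination of study treatment, a phrase that covers both ways of leaving treatment. A window without an end needs a very literal reading of one word. Confining ORR to the treatment period also leaves little room for new anticancer therapy to enter, and the PFS/DOR table already supplies the natural convention of stopping at the last assessment before new treatment.

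**ORR against DOR.** DOR is analysed in responders and must follow them past the end of treatment to observe progression. A shorter window for best response than for DOR is coherent.

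**The case for a change.** The strongest case for acting is that this sentence governs the primary endpoint, is listed in Section 7 as a clarification, and still leaves the closing point open. The success rule has no slack at the boundary between 5 and 6 responders. The trial is open-label and single-arm, and Section 8 lets the sponsor settle data handling up to database lock, so in principle the cut-off could be chosen with responses known. Clearer wording would cost one sentence and no new data.

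Part of this stands. The sentence names no date or visit, and it is silent on Cycle 8 completers and on new anticancer treatment. The step from there to lost responses does not stand, because it needs a filter that the SAP does not contain and an assessment that the SAP does not describe. The scope for choosing a cut-off is also narrow. Readings differ mainly over the discontinuation evaluation, whose name points to inclusion, and the primary result rests on central assessment by the committee (Section 5.4.1). Section 9 places derivation rules in separate documents, where mapping a visit to a window normally belongs. If responses were lost, the observed ORR would fall, so that error could not produce a false claim that the threshold was exceeded.

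**Conclusion.** No change to the plan follows. The Section 5.4 sentence lacks detail that analysts fill sensibly: assessments through the evaluation at discontinuation, or the corresponding end-of-treatment evaluation after Cycle 8, and before any new anticancer treatment. On that reading no response is lost, the rule of 6 responders in 35 is unchanged and power at a true ORR of 25% remains 90.2%.

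The lower power figures, from 89.1% down to 72.8%, apply only if the evaluation includes a tumor assessment, its results are excluded, and between 2% and 20% of responses are first documented there. The SAP establishes none of these. The conclusion assumes that the protocol, which is not shown, does not exclude the discontinuation evaluation from the response assessment.
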